### 9.2.4 Sample Size and Accrual

The PrEP Comparison Component will enroll a total of 350 (233 in Cohort 1 and 117 in Cohort 2) women over a 12-month period. Women will be followed through 26 weeks postpartum. Expected duration of follow-up for a given maternal participant is between 7 and 12 months depending on the gestational age of the pregnancy at enrollment. The following sample size and power calculations assume a final analysis sample of 300 women (200 in Cohort 1 and 100 in Cohort 2). The primary reason for the 2:1 enrollment into the two cohorts was to balance the need for a “No PrEP” comparison group (to provide the background rates for safety outcome measures) with the need for a large enough PrEP group to examine outcomes that would be restricted to women in that group (Adherence). To achieve this sample size at the analysis phase, this study will enroll ~350 women to accommodate a decrease of ~15% due to maternal attrition.

**Table 8** shows the expected precision of a range of PrEP adherence estimates across different sample sizes in Cohort 1. For example, with a sample size of 200 women in Cohort 1, the width of the 95% confidence interval for an estimated adherence rate of 75% is 13%.

**Table 8: Precision (shown as 2-sided 95% confidence intervals) of different estimates of the proportion with good adherence (for illustration, defined as meeting or exceeding the threshold corresponding to protective drug levels of TFV-DP) at different sample sizes for Cohort 1.**

% Adherent	Sample Size in Cohort 1			
	150	200	250	300
50	42-58%	43-57%	44-56%	44-56%
60	52-68%	53-67%	54-66%	54-66%
65	57-73%	58-72%	59-71%	59-70%
70	62-77%	63-76%	64-76%	65-75%
75	67-82%	68-81%	69-80%	70-80%
80	73-82%	74-85%	75-85%	75-84%

**Table 9** below shows the precision of estimates of safety outcomes (e.g. preterm birth) expected with a range of event rates and a sample size of 200 women in Cohort 1 and 100 women in Cohort 2. It is expected that the rates of these outcomes will be low particularly since this is a young group of healthy HIV uninfected women. To that end, a range of AE rates with corresponding confidence intervals is included in the protocol.

**Table 9: 95% Confidence Intervals for different possible event rates of safety outcomes in Cohort 1 (n=200) and Cohort 2 (n=100)**

Event Rate	95% Confidence Interval	95% Confidence Interval
	Cohort 1 (n=200)	Cohort 2 (n=100)
0.5%	(0, 2.8)	(0, 3.6)
2.0%	(0.5, 5.0)	(0.2, 7.0)
4.0%	(1.7, 7.7)	(1.1, 9.9)

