### Primary Objective 2.3.1:

- Women in Cohort 1 will comprise the analysis sample. A binary indicator, “optimal adherence” will be created, as defined above as TFV-DP levels in DBS meeting or exceeding the threshold determined in the PK Component as corresponding to protective levels of PrEP (24). At each visit that TFV-DP levels are obtained (see [Appendix IIA](#)), the proportion of women with optimal adherence will be calculated based on their TFV-DP levels at each visit. The proportion of visits with optimal adherence in the pregnancy vs. postpartum periods will be calculated and compared.
- Exploratory analyses identifying baseline and time-varying predictors of optimal adherence will be conducted with multivariable regression models using generalized estimating equations with a logistic link (to account for repeated measures across time for each participant).
- Adherence (as measured in TFV-DP levels) will also be summarized as a continuous outcome (median, IQR and mean [SD]) at each time point noted above when drug levels are measured, and “average” adherence across pregnancy and postpartum periods, will be calculated, using generalized estimating equations. We will focus on periods during which the participant has formally elected to be on PrEP. If a woman elects to formally stop PrEP (by notifying study personnel), periods of being formally off study drug will not be considered in adherence calculations.
- Other approaches to summarizing the adherence outcome will be considered. This includes an ordinal variable with categories corresponding to different dosing levels. For this type of outcome, at each visit that drug levels are measured in DBS, descriptive analyses will summarize the proportion of women in each adherence category, refer to categories discussed in [Section 9.1.6](#).

- Baseline characteristics, and patterns of adherence and duration on PrEP will be summarized separately for women in Cohort 2 who later decide to initiate PrEP using the approaches outlined above.
- The following additional descriptive statistics will be calculated: The proportion of women a) with at least one visit with TFV-DP levels corresponding to optimal adherence, b) who had TFV-DP levels corresponding to optimal adherence at all visits, c) who had no detectable TFV-DP levels at any visit.

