6.3 Primary Estimand(s) - PrEP Comparison Component

6.3.1 First Primary Estimand

Primary Objective 1: To characterize PrEP adherence among HIV-uninfected young women during pregnancy and for twenty-six weeks postpartum, when provided with enhanced adherence support through mobile technology and counseling based on observed drug levels.	
Estimand description	The probability that pregnant and postpartum HIV-uninfected women will have optimal adherence to daily oral PrEP 1) at defined timepoints; 2) during pregnancy and postpartum (through twenty-six weeks) as measured in TFV-DP concentration levels in dried blood spots during periods when women are formally prescribed PrEP

Treatment	
 1. Daily oral PrEP (200 mg FTC/ 300 mg TDF) during pregnancy and/or postpartum. 2. Enhanced adherence support, including SMS messaging and feedback of drug levels with tailored counseling. 3. Behavioral HIV risk reduction package
Target population	Analysis set
Women who are pregnant and HIV-uninfected, 16-24 years of age, with a confirmed singleton pregnancy of 32 weeks' gestation or less and who have access to a mobile phone, are able to receive and read SMS messages, and express willingness to take PrEP anytime between pregnancy and 26 weeks postpartum	Adherence set: Women initiating PrEP
Variable(s)	Outcome measure(s)
TFV-DP drug concentration level	
 1. TFV-DP drug concentration level from Dried Blood Spots (DBS) measured in pregnancy at 4, 8, 12, 24, 36 week study visits, Labor and Delivery, and postpartum at 6, 14, and 26 week study visits during the periods that participants are receiving PrEP. A binary indicator, "optimal adherence" will be defined as TFV-DP levels meeting or exceeding the threshold of consistent dosing of PrEP ("Green Zone") determined in the PK Component (Appendix Tables 1-2). For women who are pregnant the threshold is 600 fmol/punch if on PrEP \leq 6 weeks and 650 fmol/punch if $>$ 6 weeks; for women who are not pregnant the threshold is 700 fmol/punch if on PrEP \leq 6 weeks and 1050 fmol/punch if on PrEP $>$ 6 weeks. 2. Visits with optimal adherence according to TFV-DP level during pregnancy and during postpartum
Handling of intercurrent events	Handling of missing data

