
 • Failure to start PrEP (in Cohort I or Cohort 2/Step 2) (Treatment policy strategy) • Discontinuation of PrEP: Only visits occurring prior to discontinuation of PrEP will be included. (While on treatment strategy) • HIV seroconversion: Only visits occurring up to the later of the date of first positive HIV test or date when PrEP is discontinued will be included. (While on treatment strategy) 	
Missing data could occur in the following situations:
 
 • Missing visit(s) when adherence would have been assessed • Missing drug concentration results due to sample collection or processing issues. 
Visits without adherence data will be excluded. Sensitivity analyses will be conducted imputing "suboptimal adherence" for each missed visit/concentration result

Population-level summary measure	Analysis approach

 1. Probability of optimal adherence according to TFV-DP levels in DBS at defined times during pregnancy and postpartum 2. Probability of optimal adherence while pregnant and up to 26 weeks postpartum 	
 1. At each visit that TFV-DP levels are obtained, the binomial proportion of women with optimal adherence will be calculated bounded by an exact (Clopper-Pearson) 95% confidence interval. 2. The binomial proportion of visits with optimal adherence in pregnancy and postpartum periods during periods when women are

	formally prescribed PrEP will be calculated with exact (Clopper-Pearson) 95% confidence intervals.
--	--

Supplemental Analyses:

- Exploratory longitudinal analyses identifying baseline and time-varying predictors of optimal adherence will be conducted with multivariable regression models which account for repeated measures across time for each participant.
- Adherence (as measured in TFV-DP levels) will also be summarized as a continuous outcome measure (median, IQR and mean [SD]) at each time point noted above when drug levels are measured, and “average” drug concentrations across pregnancy and postpartum periods, will be calculated, using generalized estimating equations as appropriate. Log transformation of this outcome will be considered if the distribution is not normal.

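### SAP 6.3.1 item 2 puts exact binomial intervals on pooled visits, so with positive within-woman correlation the pregnancy and postpartum adherence intervals are too narrow

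*SAP*

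**What the plan says.** SAP section 6.3.1 (First Primary Estimand) lists two analyses.

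- **Item 1**, at each visit: "the binomial proportion of women with optimal adherence will be calculated bounded by an exact (Clopper-Pearson) 95% confidence interval".
- **Item 2**, by period: "The binomial proportion of visits with optimal adherence in pregnancy and postpartum periods", and for the time women are "formally prescribed PrEP will be calculated with exact (Clopper-Pearson) 95% confidence intervals".

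The outcome is "measured in pregnancy at 4, 8, 12, 24, 36 week study visits, Labor and Delivery, and postpartum at 6, 14, and 26 week" visits. The schedule therefore allows up to six results per woman through delivery and three postpartum.

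Repeated measures are dealt with only under Supplemental Analyses. The exploratory predictor analyses use "multivariable regression models which account for repeated measures across time for each participant", and average drug concentration uses GEE as appropriate. Nothing in item 2, or in the intercurrent-event and missing-data cells, adjusts for several visits from one woman.

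The protocol's own precision calculation for adherence (section 9.2.4, Table 8) counts women. With 200 women in Cohort 1, "the width of the 95% confidence interval for an estimated adherence rate of 75% is 13" percent.

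**The concern.** A Clopper-Pearson interval treats its denominator as independent Bernoulli trials. Item 1 meets that condition, with one result per woman at each visit. Item 2 does not, because its denominator is visits and the same woman is counted several times. If a woman who is below threshold at one visit is more likely to be below it at the next, 600 visits from 200 women carry less information than 600 separate women.

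Item 2 is one of only two stated analyses for the first primary objective, and this interval is its only statement of precision. Followed as written, the SAP would report each period's adherence with more certainty than the data hold.

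Two limits apply. The hypothesis of at least 75% concerns women rather than visits, so item 2 bears on it only indirectly. Nor does the defect by itself imply false differences between periods, because the same women appear in both.

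**Working it through.** **Inputs from the documents.** 200 evaluable women in Cohort 1 (protocol 9.2.4, SAP 2.4.2); 75% optimal adherence (Table 8); three scheduled postpartum visits and up to six through delivery (SAP 6.3.1).

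**Assumptions.** The documents give neither an ICC nor a distribution of visits per woman. I used ICC 0.1 to 0.7 and two, three or four visits each.

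**1. Reproduce the plan's figure.** Clopper-Pearson limits are the 2.5% quantile of Beta(x, n−x+1) and the 97.5% quantile of Beta(x+1, n−x). For 150/200 they are 68.4% and 80.8%, which round to Table 8's 68-81%. The unrounded width is 12.4 points; the stated 13 is the difference of the rounded limits.

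**2. The item 2 interval.** Three visits each gives 200 × 3 = 600 visits. For 450/600 the limits are 71.3% and 78.4%, width 7.1 points. Four visits each gives 600/800: 71.8-78.0%, width 6.1 points.

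**3. Allow for clustering.** Design effect DE = 1 + (m−1) × ICC, and effective n = 200m/DE. For m = 3 and ICC 0.3, DE = 1 + 2 × 0.3 = 1.6 and effective n = 600/1.6 = 375. The interval is 70.3-79.3%, width 9.0.

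| ICC | m = 3: DE, interval, width | m = 4: DE, interval, width |
|---|---|---|
| 0 (item 2) | 1.0, 71.3-78.4, 7.1 | 1.0, 71.8-78.0, 6.1 |
| 0.1 | 1.2, 71.0-78.7, 7.8 | 1.3, 71.4-78.4, 7.0 |
| 0.3 | 1.6, 70.3-79.3, 9.0 | 1.9, 70.6-79.1, 8.5 |
| 0.5 | 2.0, 69.7-79.8, 10.1 | 2.5, 69.9-79.6, 9.8 |
| 0.7 | 2.4, 69.2-80.2, 11.1 | 3.1, 69.3-80.2, 10.9 |
| 1 | 3.0, 68.4-80.8, 12.4 | 4.0, 68.4-80.8, 12.4 |

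With exactly three visits each and any non-negative ICC, the width lies between 7.1 and 12.4 points, and item 2 reports the lower end.

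**4. Coverage of the nominal 95% interval.** Beta-binomial simulation, 20,000 trials, 200 women, true proportion 60% or 75%:

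| Visits per woman | ICC 0.1 | 0.3 | 0.5 | 0.7 |
|---|---|---|---|---|
| 2 | 94% | 92% | 90% | 87-88% |
| 3 | 93-94% | 89% | 84-85% | 80-81% |
| 4 | 92% | 85-86% | 79-80% | 74% |
| 1, 2 or 3 (in 15%, 20%, 65% of women) | 94% | 90% | 86% | 82% |

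At ICC 0.02 to 0.05, coverage with three or four visits is about 94-95%.

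**5. The proposed replacement.** In the same scenarios the woman-clustered robust interval (independence working correlation, t with 199 df) covered 94.9-95.6%, uneven visits included. At a true proportion of 60% with three visits, its mean half-width was 4.3, 5.0, 5.6 and 6.1 points at the four ICCs, against 4.0 for Clopper-Pearson.

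**6. The period difference.** With four pregnancy and three postpartum visits and one exchangeable ICC, an interval for the difference that ignores clustering covered 96%, 98%, 99% and over 99.9%. It is conservative there, because the positive correlation between periods is ignored too.

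**The case against.** The strongest reply is that the size rests on an ICC the documents do not give. Drug carry-over explains little of it. At the PK Component half-lives (protocol 1.3.3.1), the fraction left after a four-week pregnancy gap is 2^(−28/15.3) = 0.28. After the postpartum gaps of 8 and 12 weeks it is 2^(−56/18.0) = 0.12 and 2^(−84/18.0) = 0.04. Drug-level feedback and thresholds that change with time on PrEP could weaken the correlation further. At very low ICC the conservatism of the exact interval nearly offsets the problem. All of this stands as a limit on the size. It does not make independence a sound default: adherence habits plausibly persist in a woman, and levels under almost fully observed dosing still varied widely (interquartile range 691-1166 in pregnancy), with the 650 threshold near the lower quartile.

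Six visits is a schedule maximum that few will approach. Weeks 24 and 36 are for early enrollers, most delivery-visit procedures need not be repeated within 30 days of the last visit, and visits after PrEP is stopped are excluded. That is right, and it is why two to four visits are used above. The 7.1 to 12.4 range also assumes exactly three visits each. With the uneven pattern, the mean is 0.15 × 1 + 0.20 × 2 + 0.65 × 3 = 2.5 visits and the range becomes about 7.8 to 13.0. The Adherence Set also includes Cohort 2 women who start PrEP later, so 200 is Table 8's denominator rather than item 2's exact one.

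Finally, the objective is descriptive, and no test or stopping rule uses this interval. That limits the consequence, but a reported 95% interval should still cover close to 95%. The SAP names the method explicitly, so the Analysis Implementation Plan cannot be assumed to change it.

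**Conclusion.** The concern holds. Item 2 specifies an interval for independent observations on data that are repeated within women, so with positive within-woman correlation each period's interval is too narrow. For two to four visits per woman, actual coverage is about 85-92% at ICC 0.3 and 79-90% at ICC 0.5. The effect is minor at ICC 0.1 with two or three visits, and close to nil at 0.05 or below. The direction needs only positive correlation; the size depends on the assumed ICC and visit counts. The point estimates, the item 1 intervals and the monitoring rules are unaffected. This should be corrected before analysis, although it does not threaten the study's main conclusions.

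**What to change.** Keep Clopper-Pearson for item 1. For item 2, keep the visit proportion as the estimate and replace the interval with one of two options:

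- a bootstrap that resamples women; or
- an intercept-only logit GEE with independence working correlation and robust variance clustered on woman.

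Name the independence working correlation explicitly. Women who stop PrEP contribute fewer visits, so another structure could shift the visit-weighted estimate. Use the same interval in the sensitivity analysis that counts missed visits as suboptimal.

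Protocol section 9.2.6 also says "The proportion of visits with optimal adherence in the pregnancy vs. postpartum periods will be calculated and compared", without naming a method. If that comparison is made, do it in one clustered analysis that keeps both periods' visits from a woman in the same cluster.

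The cost is one sentence in the SAP, with no new data and no change to the estimate. The price is wider intervals: about 1.03 to 1.7 times for two to four visits per woman and ICC 0.1 to 0.7.

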6.3.2 Second Primary Estimand

Primary Objective 2: To assess the safety of FTC/TDF for PrEP during pregnancy and postpartum by comparing pregnancy outcomes and maternal and infant safety between cohorts.	
Estimand description	Incidence rate ratio of cumulative adverse events (AEs) up to 26 weeks postpartum among PrEP exposed vs. PrEP unexposed women
Treatment	
 1. Daily oral PrEP (200 mg FTC/ 300 mg TDF) throughout follow-up. 2. Enhanced adherence support, including SMS messaging and feedback of drug levels with tailored counseling. 3. Behavioral HIV risk reduction package
Target population	Analysis set
Women who are pregnant and HIV-uninfected, 16-24 years of age, with a confirmed singleton pregnancy of 32 weeks' gestation or less and who have access to a mobile phone and are able to receive and read SMS messages	Maternal Safety Set: all enrolled maternal participants
Variable(s)	Outcome measure(s)
Occurrence of at least one of the following maternal AEs up to 26 weeks postpartum 
 • Grade 3 or higher adverse events • Grade 2 or higher chemistry abnormalities 	Outcome measures as defined by the variables (graded according to the NIAID DAIDS Table for Grading the Severity of Adult and Pediatric Adverse Events). 
 • The start of person-time for the PrEP-exposed group is study entry for Cohort 1 and Cohort 2/Step 2 entry for Cohort 2; • The start of person-time for the PrEP unexposed group is study entry (for Cohort 2 only; person-time is censored when initiating PrEP for participants enrolled in Cohort 2/Step 2)
Handling of intercurrent events	Handling of missing data

 • Failure to start PrEP (in Cohort 1 or Cohort 2/Step 2) (Treatment policy strategy) • Premature discontinuation of PrEP (Treatment policy strategy) 	Participants who discontinue follow-up before the 26-week postpartum visit will have their outcome determined based on data available until the time of discontinuation (i.e., a participant who discontinued follow-up without a prior AE is assumed not to have an AE had they been observed for the intended duration).
Population-level summary measure	Analysis approach
Incidence rate ratio (among PrEP exposed vs. PrEP unexposed women) of cumulative adverse events up to 26 weeks postpartum	Incidence rate ratio of cumulative AEs up to the week-26 postpartum visit (among PrEP exposed vs. PrEP unexposed women) estimated based on Poisson distribution (with 95% Wald CI).

Supplemental Analyses:

- Analyses will be repeated stratified by time period (i.e., antepartum (AP) and postpartum (PP), and within AP stratified by gestational age category of enrollment).
- Rates of maternal adverse events in AP and PP periods will also be calculated and compared across levels of PrEP adherence (based on TFV-DP levels in dried blood spots). Models will be fit adjusting for potential confounders.

- To compare time to first adverse event in PrEP exposed vs. PrEP unexposed women, the hazard ratio (95% CI) will be estimated with Logrank test p-value from Cox proportional hazards regression on time to first AE with PrEP exposure as a time-varying covariate.

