These findings are in contrast to results from the PROMISE trial, which demonstrated higher proportions of severe adverse pregnancy outcome in healthy HIV-infected pregnant women who received TDF-FTC-LPV/r (9%) versus ZDV-3TC-LPV/r (4%) to prevent *in utero* HIV transmission (72). The risk of very preterm delivery before 34 weeks of gestation was also significantly higher in women who received TDF-FTC-LPV/r versus ZDV-3TC-LPV/r (6.0% versus 2.6%,  $p=0.036$ ), as was the risk of infant death by Day 14 (4.4% versus 0.6%,  $p<0.001$ ). Further work is underway to better understand this finding, including whether drug interactions related to concomitant lopinavir-ritonavir may have contributed to these health outcomes. The gestational age at delivery for IMPAACT 2009 will be confirmed using obstetrical ultrasound, thus addressing an important limitation of studies thus far. The improved precision of gestational age dating will be an important contribution to the medical literature around antiretroviral drug exposure and adverse birth outcomes, without the potential confounding from HIV infection.

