PrEP for HIV prevention has been shown to be highly efficacious among MSM, heterosexual men and women, serodiscordant couples and injection drug users (10-12, 45). While pregnant women have been excluded from enrollment into PrEP trials, very high rates of pregnancy (range 3.9 to 52 per 100 person years) have occurred among participants in HIV prevention trials despite ready access to effective contraception (141, 145, 146). In the case of incident pregnancy, PrEP trial participants were instructed to stop study drug immediately, at an average gestational age of 6 weeks (147). Data from these incident pregnancies as well as the registry data show that risk for toxicity appears to be low and neither pregnancy nor breastfeeding is considered a contraindication for PrEP initiation per the CDC and WHO clinical guidelines (148). Exposure to PrEP in early pregnancy, for example, was not associated with detectable differences in later pregnancy outcomes (147). The PrIYA PrEP implementation program in Kenya recorded no observed difference in pregnancy outcomes among women with prenatal PrEP use(149). In addition, the recommended regimen for PrEP, FTC/TDF, has been used safely for treatment of pregnant women with chronic hepatitis B infection as well as pregnant women with HIV for over a decade and forms the backbone of the first line treatment regimen recommended by the World Health Organization (WHO) (82, 150-153).

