### **6.3.3 Maternal HIV Seroconversion: Management of Maternal Participants at Every Visit (PrEP Comparison Cohort only)**

Maternal participants in the PrEP Comparison Component with confirmed HIV infection will remain on-study and continue to be followed through scheduled study exit per the applicable SoE ([Appendix IIA](#) or [IIB](#)). However, because they will no longer be on PrEP, the following procedures will no longer be performed among these participants:

- Rapid HIV test
- Study drug dispensing
- iNSC with drug level feedback
- Two-way SMS support (one-way SMS support should continue)
- PrEP acceptability assessment
- TFV-DP (DBS) level

In addition, ALT, creatinine, CrCl and HIV RNA testing will be performed at a decreased frequency—approximately every six months during scheduled study visits—to monitor chemistries and HIV viral load among these participants.

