Regardless of cohort, all maternal participants will follow similar schedules of evaluations through the course of pregnancy and in the 26 weeks following delivery. Women in Cohort 2 may choose to initiate PrEP at any stage following study entry, and triggers for change in PrEP perceptions and acceptability over time will be recorded to better understand women's motivation to seek additional HIV prevention services. As Cohort 2 is not exposed to antiretroviral agents during pregnancy or postpartum, its unexposed time period will serve as a comparison group for estimates of incidence and prevalence of maternal and infant safety outcomes including a) pregnancy outcomes, b) maternal adverse events, and c) infant growth and development between the two exposure groups.

The primary objectives focus on women who initiate PrEP during pregnancy and continue through the first 26 weeks postpartum (Cohort 1). Adherence to PrEP will be assessed by measuring TFV-DP drug levels in dried blood spots. Participants in this arm will receive an intervention designed to provide participant-centered support, including support for PrEP use/adherence, comprised of a) two-way SMS messaging related to PrEP adherence, and b) targeted adherence counseling guided by TFV-DP drug levels.

Maternal participants who change their intent regarding PrEP will be allowed to do so. Participants in Cohort 1 who choose to stop PrEP will continue in follow-up. Maternal participants

in Cohort 2 who subsequently choose to initiate PrEP will undergo a Step Change, and will be referred to as Cohort 2/Step 2 and will follow the procedures for Cohort 1/Cohort 2 Step 2. While a formal step change will only be required when those originally declining PrEP later chose to initiate it, there is no upper limit set on the number of switches allowed for each participant. Switching will be closely monitored as part of feasibility and adherence outcomes.

There will be no randomization for this study. To monitor the balance of the maternal participants enrolled among various groups, the enrollment will be stratified by:

- Cohort: PrEP vs. No PrEP at enrollment
- Trimester of enrollment during pregnancy: 1st or 2nd trimester vs. 3rd trimester
- Country
- Age at enrollment: 16-17 years vs. 18 years of age and older

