6.3.4 Fourth Primary Estimand

Primary Objective 2: To assess the safety of FTC/TDF for PrEP during pregnancy and postpartum by comparing pregnancy outcomes and maternal and infant safety between cohorts.	
Estimand description	Incidence rate ratio of cumulative adverse events up to the age 26-week visit among PrEP exposed vs. PrEP unexposed infants
Treatment	
Infants exposed to the following maternal treatment in utero and/or through breastfeeding:
 
 1. Daily oral PrEP (200 mg FTC/ 300 mg TDF) throughout follow-up. 2. Enhanced adherence support, including SMS messaging and feedback of drug levels with tailored counseling. 3. Behavioral HIV risk reduction package
Target population	Analysis set
Infants born to women who are pregnant and HIV-uninfected, 16-24 years of age, with a confirmed singleton pregnancy of 32 weeks' gestation or less and who have access to a mobile phone and are able to receive and read SMS messages	Infant Safety Set: all enrolled infants
Variable(s)	Outcome measure(s)
Infant adverse events: 
 • Infant death within the first 26 weeks of life • Infant Grade 3 or higher adverse events reported between birth and the age 26-week visit. 	Outcome measures as defined by the variable (graded according to the NIAID DAIDS Table for Grading the Severity of Adult and Pediatric Adverse Events). The start of person-time for the PrEP-exposed group is birth for Cohort 1 and birth or Cohort 2/step 2 entry (whichever is later) for Cohort 2; The start of person-time for the PrEP unexposed group is birth (Cohort 2 participants only; person-time is censored when initiating PrEP for participants enrolled in Cohort 2/Step 2).
Handling of intercurrent events	Handling of missing data

 • Mother's failing to start PrEP (in Cohort 1 or Cohort 2/Step 2) (Treatment policy strategy) • Mother's discontinuation of PrEP (Treatment policy strategy) 	Participants who discontinue follow-up before the age 26-week visit will have their outcome determined based on data available until the time of discontinuation (i.e., a participant who discontinued follow-up without a prior AE is assumed not to have an AE had they been observed for the intended duration).
Population-level summary measure	Analysis approach

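### The four safety estimands do not name HIV seroconversion, so Cohort 2 women who acquire HIV and start ART, and their infants, stay in the PrEP-unexposed comparator

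*SAP*

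**What the plan says.** For adherence (SAP 6.3.1) the plan sets a rule: "HIV seroconversion: Only visits occurring up to the later of the date of first positive HIV test or date when PrEP is discontinued" count, under a while-on-treatment strategy.

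For safety, the intercurrent-event rows of SAP 6.3.2 (maternal adverse events), 6.3.3 (pregnancy outcome), 6.3.4 (infant adverse events) and 6.3.5 (infant growth and development) list two events only: not starting PrEP and stopping PrEP, both under treatment policy. In 6.3.2 unexposed follow-up starts at study entry for Cohort 2, and "person-time is censored when initiating PrEP for participants enrolled in Cohort 2/Step 2". Section 6.3.4 has the same rule, starting at birth. In 6.3.5 an infant is unexposed if the mother has never used PrEP.

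SAP 2.1.2 justifies the comparator this way: "As Cohort 2 is not exposed to antiretroviral agents during pregnancy or postpartum", its unexposed time serves for comparison.

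The protocol describes what follows an infection. Women in the PrEP Comparison Component stay on study to scheduled exit (6.3.3), as do their infants (6.3.4). Sites must plan for ART to begin within days of diagnosis (6.3). After infection, "ALT, creatinine, CrCl and HIV RNA testing will be performed at a decreased frequency", about every six months (6.3.3). Section 1.3.1 describes FTC/TDF as the core of the WHO-recommended first-line regimen.

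**The concern.** Neither listed intercurrent event can happen to a Cohort 2 woman who never takes PrEP. If she acquires HIV, nothing in 6.3.2 to 6.3.5 changes her status or her infant's. Read as written, the SAP counts follow-up with HIV infection and antiretroviral treatment as PrEP-unexposed. That conflicts with 2.1.2, and with 6.3.3, whose estimand is worded for HIV-uninfected pregnant women but has no rule for infection before delivery.

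The protocol's own background suggests that ART can move these endpoints. Section 1.2 reports severe adverse pregnancy outcomes of 9% versus 4%, and infant deaths by Day 14 of 4.4% versus 0.6%, between two ART regimens. It also reports lower newborn bone mineral content with maternal triple therapy than with zidovudine alone. If PrEP protects against HIV, these infections will be more frequent in the comparator than in the PrEP group. The choice between keeping and censoring such follow-up would then be made after the data are seen, in a primary safety analysis.

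**Working it through.** **Inputs.** HIV incidence r, from Protocol 1.3.1: 2.31 (a cohort of pregnant young women), 3.6 and 3.8 (two meta-analyses), and 5-6% in prevention trials, read here as per year. Cohort 2 size N = 100 evaluable or 117 enrolled, and follow-up T = 7 to 12 months (Protocol 9.2.4). All counts assume no switching to PrEP.

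**1. The plan's own figure.** Table 10 states 80% power for 10% (n=100) versus 23% (n=200). A two-sided two-proportion calculation at alpha 0.05 without continuity correction gives 80.6%. The six rows of Table 10 give 77.8% to 80.6%. The design figure is reproduced.

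**2. What the text does with a seroconverter.**

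| Group | Rule that applies | Result |
|---|---|---|
| Cohort 1, Step 2 | Infection stops PrEP (Protocol 6.3.1, 8.3); stopping PrEP is treatment policy | Kept as exposed, by a stated rule |
| Cohort 2, never on PrEP | None; unexposed time is censored only at PrEP start | Kept as unexposed, strategy not named |
| Infant of the Cohort 2 woman | Defined by maternal PrEP only (6.3.4, 6.3.5) | Kept as unexposed |

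**3. Expected Cohort 2 seroconversions over full follow-up**, N × (1 − exp(−rT)):
- Low: 100 × (1 − exp(−0.0231 × 7/12)) = 1.3
- At 3.8: from 2.2 (N=100, 7 months) to 4.4 (N=117, 12 months)
- High: 117 × (1 − exp(−0.06 × 1)) = 6.8

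The chance of at least one, 1 − exp(−NrT), runs from 74% to 99.9%.

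**4. Before delivery only** (6.3.3 and the birth measures in 6.3.5). Taking about 6 postpartum months from 7 to 12 leaves roughly 1 to 6 antepartum months:
- 100 × 1/12 × 0.036 = 0.3
- 117 × 0.5 × 0.038 = 2.2

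**5. Share f of unexposed maternal person-time after infection**, 1 − (1 − exp(−rT))/(rT):
- r = 0.0231, T = 7/12: 0.7%
- r = 0.06, T = 1: 2.9%

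Infant time starts at birth, so antepartum infections affect all of it. With antepartum time A and B = 0.5 year, the share is 1 − exp(−rA) × (1 − exp(−rB))/(rB):
- r = 0.0231, A = 1/12: 1 − 0.9981 × 0.9942 = 0.8%
- r = 0.06, A = 0.5: 1 − 0.9704 × 0.9851 = 4.4%

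**6. Effect on the maternal rate ratio.** If the true ratio is R and the post-infection rate is m times the unexposed rate, the observed ratio is R/((1 − f) + f × m). Assume R = 2.3 (23%/10% in Table 10):
- m = 2.3: 2.28 at f = 0.67%, and 2.21 at f = 3%
- m = 5, f = 3% (assumed): 2.05

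**7. Effect on power for 10% versus 23%.** If 1% to 6% of Cohort 2 carried the Cohort 1 risk, power would be 79.6% to 74.4%. If those women were removed instead, it would be 80.3% to 78.7%.

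**The case against.** The strongest reply is that the handling can be deduced. The safety sets contain all enrolled women and all liveborn infants, so a programmer would keep seroconverters. That amounts to treatment policy, a legitimate strategy for safety. It also fits the protocol's instruction to keep infants of infected mothers on study for safety monitoring. This stands in part. Retention is defensible, but the SAP does not name it for Cohort 2, and it contradicts the premise in 2.1.2. The Analysis Implementation Plan, which was not available, may say more, but the SAP is where intercurrent events are defined.

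A second reply stands in full. Censoring at infection conditions on an event that PrEP itself affects and removes women unevenly from the two groups, so it may be informative. Censoring is therefore not clearly the better primary analysis.

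A reader might draw stronger conclusions that the documents do not support:
- **That the gap hides a PrEP harm.** Events from HIV or ART would raise comparator rates, but sparser ALT and creatinine testing after infection lowers detection of Grade 2 or higher chemistry events. The net direction is unknown.
- **That comparator rates shift by 2 to 4 percentage points.** This needs two to four seroconverters per 100 women, each with an extra event. Under assumed values (4 seroconverters, half of follow-up after infection, 5% background, fivefold risk), the excess is 4 × 0.5 × (25% − 5%) = 0.4 events.
- **That these women certainly take tenofovir.** It is probable from Protocol 1.3.1, but ART comes from non-study sources and no regimen is specified.
- **That the protocol promises no HIV-related confounding.** Its phrase "without the potential confounding from HIV infection" contrasts enrolling uninfected women with earlier work in HIV-infected women. It does not say that nobody will seroconvert.

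**Conclusion.** The point holds as a gap in the estimand definitions, mainly for Cohort 2. The plan recognises seroconversion for adherence but not for safety, and as written it leaves HIV-infected, ART-treated follow-up in a comparator justified by having no antiretroviral exposure. At least one such case is likely. The count of about 1 to 7 women rests on the cited incidences applying to Cohort 2 and on no switching to PrEP; its upper end also takes 12 months for every enrolled woman with no attrition. The usual effect on the rate ratio is small, and this is not a power failure. The exposure is greatest where comparator events are few. As an illustration, if two comparator events became three, the ratio would be multiplied by 2/3. Infant death could be in that position.

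**What to change.** - Name maternal HIV seroconversion in the intercurrent-event rows of SAP 6.3.2 to 6.3.5 and state the strategy.
- Pre-specify an analysis that, in both exposure groups, censors maternal and infant person-time at the mother's first positive HIV test (6.3.2, 6.3.4) and excludes outcomes that occur or are measured after that date (6.3.3, 6.3.5).
- Report it beside the treatment-policy version, and state in advance which is primary.
- Amend SAP 2.1.2 to say that Cohort 2 is unexposed to antiretrovirals unless a woman starts PrEP, or seroconverts and starts ART.

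The cost is SAP wording and one further set of estimates. All HIV test results already go onto eCRFs (Protocol 7.2.1 and 7.2.2). A few woman-months leave the censored analysis, and that censoring may be informative, which is the reason for showing both versions.
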